- If the day of medication date is missing, but the month and year are equal to the start of randomized treatment, then the medication date will be replaced by the start of randomized treatment. For example, if the medication start date is --/JAN/2015, and randomized treatment start date is 15/JAN/2015, then the imputed medication start date will be 15/JAN/2015.
- If both the day and month of medication start date are missing but the start year is equal to the start of randomized treatment, then the medication date will be replaced by the start of randomized treatment. For example, if the medication start date is --/--/2014, and randomized treatment start date is 19/NOV/2014, then the imputed medication start date will be 19/NOV/2014.
- In all other cases the missing medication day or month will be replaced by 1.
- Incomplete stop date will be replaced by the last day of the month (if day is missing only), if not resulting in a date later than the date of subject's death. In the latter case the date of death will be used to impute the incomplete stop date.
- In all other cases the incomplete medication stop date will not be imputed.

Subsequent anti-cancer therapy

Incomplete subsequent anti-cancer therapy start dates will be imputed as follows:

- If only day is missing, it will be imputed as the last day of the month unless the end date of subsequent anti-cancer therapy is before that date. In that case, the incomplete anti-cancer therapy start date will be imputed as the end date of the anti-cancer therapy.
- If both day and month are missing, no imputation will be performed.

Exposure

- In case the study drug start date is missing, no imputation will be performed.
- In case the last date of study drug is incomplete the date of last administration of study drug will be taken from the treatment termination eCRF pages.

Date of last dose of study drug if unknown or partially unknown will be imputed as follows:

- If the last date of study drug is completely missing and there is no End of Treatment eCRF page and no death date the subject should be considered to be ongoing and use the last dosing date on or prior to the cut-off date for the analysis as the last dosing date
- If the last date of study drug is completely or partially missing and there is either an End of Treatment eCRF page or a death date available (within the cut-off date) then imputed last dose date:
 - = 31DECYYYY, if only Year is available and Year < Year of min (EOT date, death date)

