14.2 Subsequent Anti-Cancer Therapies/Procedures

Subsequent anti-cancer treatment will be provided in a data listing with data retrieved from “Anti-Cancer Treatment after Discontinuation Details”, “Radiotherapy after Discontinuation”, and “Surgery after Discontinuation” eCRF pages. The earliest date of start of new anti-cancer *drug* therapy will be used for the definition of the on-treatment period; the earliest date of start of any new anti-cancer therapy will be used for censoring for efficacy analyses.

15 Treatment Compliance and Exposure

Analysis sets: FAS / Safety analysis set

All dosing calculations and summaries will be based on “Avelumab Administration Details” eCRF pages.

Subjects will receive an IV infusion of avelumab at a dose of 10 mg/kg (over the duration of 1 hour [-10 minutes / +20 minutes, that is, over 50 to 80 minutes]) once every 2 weeks (one cycle). Analysis of exposure will be based on the calculated actual dose levels (total dose administered/weight, mg/kg). The last available weight of the subject within 3 days prior to the day of dosing will be used.

In case of missing total dose, the dose level as entered in the eCRF will be used.

The duration of therapy (in weeks) during the study is defined as:

$$\text{duration} = \left(\frac{\text{date of last dose} - \text{date of first dose} + 14}{7} \right)$$

The cumulative dose (mg/kg) per subject in a time period is the sum of the actual dose levels that the subject received within that period (i.e. total dose administered (mg) / weight (kg)).

Each cycle is defined by a 2-week period. The dose intensity and the relative dose intensity will be calculated for each subject across all cycles. The dose intensity (mg/kg/cycle) per cycle is defined as

$$\text{dose intensity} = \left(\frac{\text{Cumulative dose}}{(\text{duration of therapy (in weeks)})/2} \right)$$

The relative dose intensity is defined as the actual dose intensity divided by the planned dose per cycle.

The summary of treatment exposure and compliance table will include the following information:

- Duration of therapy (weeks)
- Total number of infusions received
- Cumulative dose of therapy (mg/kg)
- Dose intensity (mg/kg/cycle)
- Relative dose intensity of therapy (%)

A listing of treatment exposure and compliance will also be created to summarize the information listed above for each subject.

Partial Doses

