16.2.2 Best Overall Response and Objective Response

The confirmed BOR is defined as the best confirmed response obtained among all tumor assessment visits after start of study treatment until documented disease progression, taking requirements for confirmation into account as detailed in [Section 16.1.1](#). In addition, the minimum duration for a BOR of SD is defined as at least 6 weeks after start of study treatment. A BOR of PD requires that progression is observed ≤ 12 weeks after first dose of study treatment (and not qualifying for CR, PR or SD).

Only tumor assessments performed before the start of any further anti-cancer treatment will be considered in the assessment of BOR. Clinical deterioration will not be considered as documented disease progression. If a tumor assessment was performed on the same day as the start of a new anti-cancer therapy, it is assumed that the tumor assessment was performed prior to the start of the new anti-cancer therapy; therefore, this tumor assessment is included in the assessment of BOR.

The tumor response at each assessment visit will be determined according to RECIST 1.1 and as adjudicated by an IERC. In case of different dates of scans within the same tumor assessment visit, the date of assessment is determined by the IERC as specified in the Charter.

The objective response rate (ORR) is defined as the proportion of subjects having reached a confirmed BOR of CR or PR according to RECIST 1.1 and as determined by the IERC.

[Table](#) summarizes the derivation rules described by [Eisenhauer, et al.](#) for the BOR when confirmation from subsequent assessment is needed (5).

Table 3 Best Overall Response When Confirmation of CR/PR Is Required

| Overall response 1st time point | Overall response subsequent time point | Best overall response (BOR) |
|------------------------------------|---|---|
| CR | CR | CR |
| CR | PR | SD, PD or PR ^a |
| CR | SD | SD provided minimum criteria for SD duration met; otherwise, PD |
| CR | PD | SD provided minimum criteria for SD duration met; otherwise, PD |
| CR | NE | SD provided minimum criteria for SD duration met, otherwise NE |
| PR | CR | PR |
| PR | PR | PR |
| PR | SD | SD |
| PR | PD | SD provided minimum criteria for SD duration met, otherwise, PD |
| PR | NE | SD provided minimum criteria for SD duration met, otherwise NE |
| NE | NE | NE |

CR = complete response, PR = partial response, SD = stable disease, PD = progressive disease, NE = non-evaluable.

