16.2.3 Duration of Response

DR is defined, for subjects with a confirmed objective response according to RECIST 1.1, as the time from first documentation of objective response (CR or PR) to the date of first documentation of objective PD or death due to any cause. If a subject has not had an event (PD or death), DR is censored at the date of last adequate tumor assessment. The censoring rules for DR are described in Section 16.2.4 for PFS.

DR (months) = (date of event or censoring – date of first objective response + 1)/30.4375

The Kaplan-Meier method will be used to estimate parameters for duration of response. Kaplan-Meier estimates (product-limit estimates) will be presented together with a summary of associated statistics including corresponding two-sided 95% CIs. In particular, the proportion of duration of responses at 3, 6 and 12 months will be estimated with corresponding two-sided 95% CIs. The CIs for the median will be calculated according to [Brookmeyer and Crowley \(2\)](#) and CIs for the survival function estimates at the above defined time points will be derived using the log-log transformation according to [Kalbfleisch and Prentice \(3\)](#) (CONFTYPE = loglog default option in SAS PROC LIFETEST). The estimate of the standard error will be computed using Greenwood's formula.

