16.2.4 Progression Free Survival

The PFS time, according to the RECIST 1.1, is defined as time from first administration of study treatment to the date of the first documentation of objective PD or death due to any cause, whichever occurs first.

PFS time (in months) is defined as:

$$(\text{date of event or censoring} - \text{date of first dose of study treatment} + 1) / 30.4375$$

PFS data will be censored on the date of the last adequate tumor assessment for subjects who do not have an event (PD or death), for subjects who start a new anti-cancer therapy prior to an event or for subjects with an event after two or more missing tumor assessments. Subjects who do not have a baseline tumor assessment or who do not have any post-baseline tumor assessments will be censored on the date of the first study treatment unless death occurred on or before the time of the second planned tumor assessment in which case death will be considered an event. Details on determination of the first disease progression date are specified in the IERC charter.

If a tumor assessment was performed on the same day as the start of a new anti-cancer therapy, it will be assumed that the tumor assessment was performed prior to the start of the new anti-cancer therapy; therefore, this tumor assessment will be included in the derivation of the PFS time.

The censoring and event date options to be considered for the PFS and DR analysis are presented in [Table 4](#). Last adequate tumor assessment is defined as tumor assessment result that is not “NE” or “NA”.

Table 4 Outcome and Event Dates for PFS and DR Analyses

| Scenario | Date of event / censoring | Outcome |
|--|--|---|
| No baseline assessment | Date of first study treatment | Censored ^a |
| Progression or death \leq xx weeks after last tumor assessment or \leq xx weeks after treatment start date, where xx is 12 weeks through 12 months from start of treatment, and 24 weeks thereafter. | Date of progression or death | Event |
| Progression or death $>$ xx weeks after the last tumor assessment, where xx is 12 weeks through 12 months from start of treatment, and 24 weeks thereafter. | Date of last adequate tumor assessment | Censored |
| No progression | Date of last adequate tumor assessment | Censored |

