| Treatment discontinuation due to “Disease progression” without documented progression | Not applicable | Information collected on treatment discontinuation page is ignored since outcome should be derived based on documented progression only. General censoring rule is applied. |
| New anti-cancer therapy given | Date of last adequate tumor assessment before anti-cancer therapy is given | Censored |

^a However if the subject dies \leq 12 weeks after treatment start date the death is an event with date on death date.

The analysis of PFS will be performed using a Kaplan-Meier method with the same approach as for duration of response described in [Section 16.2.3](#). Kaplan-Meier estimates (product-limit estimates) will be presented together with a summary of associated statistics including corresponding two-sided 95% CIs. In particular, the proportion of PFS at 3, 6 and 12 months will be estimated with corresponding two-sided 95% CIs.

Frequency (number and percentage) of subjects with each event type (PD or death) and censoring reasons will be presented. Censoring reasons are as follows, presented in a hierarchical manner:

- No baseline assessment
- No post baseline assessments
- Start of new anti-cancer therapy
- Event after 2 or more missing assessments
- Withdrawal of consent to continuing tumor assessment
- Lost to follow-up
- Ongoing in the study without an event

The PFS time or censoring time and the reasons for censoring will also be presented in a subject listing.

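### Part B's month-end imputation of a partly dated new-therapy start can keep scans taken on the next therapy; for ORR and DRR that error only goes upward, though it is probably small

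*SAP*

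**What the plan says.** All SAP references are to the Part B SAP.

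- **Section 11, subsequent anti-cancer therapy.** For a start with no day: "If only day is missing, it will be imputed as the last day of the month", unless the therapy ended before then; in that exception the end date is used. Either branch gives the latest start the record allows. For year-only dates: "If both day and month are missing, no imputation will be performed".
- **Section 14.2.** Two start dates are derived. The earliest new drug therapy bounds the on-treatment period, and "the earliest date of start of any new anti-cancer therapy will be used for censoring for efficacy analyses".
- **Section 16.2.2.** "Only tumor assessments performed before the start of any further anti-cancer treatment will be considered in the assessment of BOR".
- **Sections 16.2.3 and 16.2.4.** "The censoring rules for DR are described in Section 16.2.4 for PFS". Table 4 then censors a subject given new therapy at "Date of last adequate tumor assessment before anti-cancer therapy is given".
- **Same-day scans (16.2.2 and 16.2.4).** "If a tumor assessment was performed on the same day as the start of a new anti-cancer therapy", the scan is taken to have come first and is kept.
- **Section 16.1.** A censored DR that reaches 6 months is a success in the DRR; a shorter one is a failure.
- **Protocol Section 7.1.5.** Part B subjects who end treatment without PD go on being scanned until PD. New therapy is not named as a reason to stop, so scans on the next therapy can exist.

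The readable text gives no separate imputation for efficacy and no sensitivity analysis for partial therapy dates.

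**The concern.** One imputation rule feeds two uses that are cautious in opposite directions. For the on-treatment safety window a late start is cautious, because it keeps adverse events in. For efficacy a late start is lenient: a scan taken between the true start and month-end is treated as if it came before the switch. That works against Section 16.2.2, which is meant to shut such scans out. Through DR it reaches the primary endpoint of the part that Protocol Section 5.1 describes as confirmatory for some approvals.

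**Working it through.** **1. The plan's own figures.** Exact (Clopper-Pearson) limits reproduce: 45/112 = 40.2% (31.0; 49.9), and the historical 11/62 = 17.7% (9.2; 29.5). With a true DRR of 45%, a lower limit above 20% needs at least 32 successes (probability 0.9999), and above 30% at least 44 (0.9055). These match the stated figures of over 99% and 90%.

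**2. How late the imputed start can be.** Shift = last day of month minus true day, so 0 to 30 days. If true starts are spread evenly over the month (an assumption), the mean is 14.7 days.

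**3. Chance that a scan falls in that gap, given a missing day.** Mean shift divided by scan interval:
- 6-weekly scans (to 12 months): 14.7/42 = 0.35; range 0 to 30/42 = 0.71.
- 12-weekly scans (thereafter): 14.7/84 = 0.175, about 18%; range 0 to 30/84 = 0.36.

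**4. What one kept scan can do to DRR.** Section 16.2.3 gives DR = (days from first response + 1)/30.4375. On the 6-week grid:
- fourth scan after response, day 168: 169/30.4375 = 5.55 months, failure;
- fifth scan, day 210: 211/30.4375 = 6.93 months, success.

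The day-210 scan decides. It is wrongly kept only if the true start came before it by no more than 30 days, so the switch lies about 180 (210 − 30) to 210 days after response, or 180/30.4375 = 5.9 to 210/30.4375 = 6.9 months. The kept scan need not be free of progression: if it shows PD, DR runs to that PD date and still passes 6 months.

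**5. What a missing day cannot do.** The shift is at most 30 days and confirmation needs at least 5 weeks (35 days). A first response and its confirmation therefore cannot both fall in the gap. A kept scan can supply the confirming assessment, or lengthen the duration.

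**6. Direction.**
- ORR and DRR: a later cut-off adds scans after those already counted. It can add a confirmation or lengthen DR, but cannot undo a confirmed response or shorten DR. The error is upward only.
- Kaplan-Meier DR and PFS: a kept scan without PD moves censoring later, while a kept PD scan turns a censored subject into an event. The curve can move either way.

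**7. Size per subject.** 1/112 = 0.9 percentage points. Starting from the SAP's example of 45/112, removing one success gives 44/112 = 39.3% (30.2; 49.0), and removing two gives 43/112 = 38.4% (29.4; 48.1). The SAP presents 45/112 as excluding the historical upper bound of 29.5%; 43/112 would not. This shows sensitivity and is not a forecast.

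**8. Year-only dates.** Section 11 supplies no date and Section 16.2.4 does not say how such a subject is censored. If the date is treated as missing, there is nothing to cut on, and scans on the next therapy could count up to PD or data cut-off.

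**The case against.** The strongest reply is that the route to a DRR flip is narrow, and that is right. It needs a confirmed responder by IERC, no IERC progression before the switch, a partial date, and a kept scan that crosses 6 months. On the 6-week grid, a subject flipped by a missing day had already gone about 6 months or more from response to switch. Section 7.1.3 of the protocol asks for the End-of-Treatment visit before new therapy where possible, Section 11 flags imputed values in listings, and Part B estimates DRR without a formal test. These points limit the size. They do not supply an efficacy date or remove the one-way direction.

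A reader might infer more than the documents support:
- **That all four measures are biased upward.** Only ORR and DRR are; kept PD scans become events in DR and PFS.
- **That 35% is a misclassification rate.** It is the chance that a scan falls in the gap, given a missing day. Most such scans would not change durable-response status.
- **That a year-only subject is never cut and the error has no bound.** Table 4 is triggered by new therapy being given, so the SAP may intend censoring even without an imputed date; it is silent on how. Any error ends at PD or data cut-off, and no subject adds more than 0.9 points to DRR.

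It is also fair to say that an earliest-date rule errs the other way. For a year-only date it could discard several valid scans taken after avelumab stopped but before the switch.

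**Conclusion.** The point stands as a minor one and a cheap improvement. The Part B SAP applies the latest possible start of new therapy to efficacy censoring, which can keep scans that Section 16.2.2 excludes, and it leaves the year-only case undefined. For ORR and the primary DRR the resulting error can only be upward; for Kaplan-Meier DR and PFS the direction is open.

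The likely effect is small: 0.9 points of DRR per flipped subject, with a flip from a missing day on the 6-week grid confined to switches about 180 to 210 days after response. The 35% and 18% rest on starts spread evenly over the month and on scans at the scheduled intervals. The number of partial dates is not in the documents, so neither the expected number of flips nor the total bias can be computed. The year-only consequence rests on the assumption that an unimputed date is handled as missing.

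**What to change.** In Section 11, keep the month-end rule for the on-treatment period only. For BOR, DR, DRR and PFS, impute the start of new therapy as the later of (a) the first of the known month, or 1 January if only the year is known, and (b) the day after the last avelumab dose. With a known month, no scan taken after the true start is then kept because of the imputation. The year-only case also gets a defined rule. The structure follows the SAP's own rule for partial death dates, which takes the later of last contact and the first of the month or year. Report DRR under the current rule as a sensitivity analysis.

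The cost is about two sentences, a second imputation and one extra DRR line; Section 14.2 already separates the safety and efficacy start dates. The downside is that some valid scans before the switch will be dropped, possibly several for a year-only date, which slightly lowers DRR. Showing DRR both ways makes that visible.

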2.3.2 Independent Endpoint Review Committee

The Independent Endpoint Review Committee (IERC) will be composed of a minimum of 3 members for Part A, and a minimum of 4 members for Part B. The role of the IERC will be to review radiographic image findings and physical findings (skin lesion mapping / physical assessments) for the determination of the BOR and date of disease progression for each subject. The full membership, mandate, and processes of the IERC will be detailed in the IERC charter for Part A, which is a single radiology review and two-oncologist review committee, and for Part B, which is a double radiology review with adjudication and single oncologist review.

3 Background Information

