7.3 Assessment of Efficacy

All radiographic images and physical findings including photographs (skin lesion mapping) and physical assessments used for the determination of disease progression must be submitted to the IERC vendor and will be reviewed by an IERC (see Section 5.1.2.2). The IERC will make the determination as to whether the criteria for tumor response or progression according to RECIST 1.1 have been met.

For each subject, tumor response assessment will be performed by CT scan or MRI (if MRI is used, CT of chest is mandatory; for trial sites in Germany, only MRI is to be used) imaging of the chest/abdomen/pelvis at a minimum plus other anatomical sites as specifically required) and other established assessments of tumor burden if CT / MRI imaging is insufficient for the individual subject. All the scans performed at baseline and other imaging performed as clinically required (other supportive imaging) need to be repeated at subsequent visits. In general, lesions detected at baseline need to be followed using the same imaging methodology and preferably the same imaging equipment at subsequent tumor evaluation visits. If lesions are no longer detectable, the same anatomical sites evaluated at baseline must be followed at every tumor assessment visit using the same imaging and photography methods as used at baseline.

An examination for clinical lesions, including mapping of skin lesions, should also be conducted at each tumor assessment. For skin lesions to be identified as target lesions, a minimum longest diameter of 10 mm is required. In the case of skin lesions, documentation by color photography using standardized procedures, including an accurate measurement scale within the image, is required. Refer to [Appendix IV](#) for standardized photography procedures with detailed requirements for lesion selection and photographic image acquisition. Clinical lesions will be considered measurable only when they are superficial and visible (for example, skin nodules, palpable lymph nodes). Skin lesions can be used as target lesions using measurements by caliper if they fulfill RECIST 1.1 for target lesions. The presence of new cutaneous lesions will be considered diagnostic of progression for RECIST 1.1, and any lesions detected by physical examination only should be documented by photography.

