8.3 Endpoints

8.3.1 Primary Endpoint

The primary endpoint for Part A of the trial is the confirmed BOR, per RECIST 1.1, as determined by an IERC and defined as the best response obtained among all tumor assessment visits after start of trial treatment until documented disease progression, excluding assessments after start of subsequent anticancer therapy, taking into account the following requirement for confirmation: PR or CR needs to be confirmed at a subsequent tumor assessment, preferably 6 weeks after the initial observation of response and according to the normal 6-week assessment schedule (or a subsequent assessment for PR), but no sooner than 5 weeks after the initial documentation of CR or PR.

For Part B, the primary endpoint is durable response, defined as objective response (CR or PR) according to RECIST 1.1, determined by an IERC, with a duration of at least 6 months. Duration of response will be calculated as specified in Section 8.3.2. Subjects for whom the duration of response is censored will be treated as failures (successes) in the analysis of durable response if the censored duration of response is below (at least) 6 months, respectively.

The date of a tumor assessment is defined as the earliest lesion measurement date corresponding to the respective visit that is documented in the eCRF. Details of determination of tumor response date at each time point will be provided in IERC charter document.

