8.3 Final Analysis

All planned analyses outlined in this SAP will be performed for the primary analysis. A partial database lock will be performed for the interim and primary analyses. The full DB lock will take place 5 years after the last subject receives the last dose of avelumab, or when the last subject dies, whichever occurs first.

In addition, no database can be locked until this SAP has been approved.

Subjects follow-up for progression and survival will continue until 5 years after the last subject receives the last dose of avelumab, or when the last subject dies, whichever occurs first. Under some circumstances, subjects may not be followed for 5 years for survival in this study, for example, subjects may be offered to enroll into a rollover study, or the Sponsor may terminate the study early.

9 Changes to the Planned Analyses in the Clinical Trial Protocol

The statistical methods as described in the protocol for Part B of this study were adopted.

10 Analysis Sets

Screening Analysis Set

The screening analysis set includes all subjects who signed the informed consent.

Full Analysis Set / Safety Analysis Set

Full analysis set (FAS) / Safety analysis set will include all subjects who received at least one dose of study drug.

Per Protocol Analysis Set

The Per-Protocol (PP) analysis set is a subset of the FAS and includes all FAS subjects who meet all of the following criteria that could impact the key objectives of the study:

- Measurable disease per RECIST 1.1 and IERC assessment
- Distant metastatic disease
- No prior anti-cancer therapy for metastatic disease
- No prior therapy with any antibody/drug targeting T-cell coregulatory proteins such as anti-PD-1, CCI, or anticytotoxic T-lymphocyte antigen-4 (CTLA-4) antibody
- Histologically proven MCC with confirmation of the diagnosis by immuno-histochemistry detection of CK20 (or other appropriate cytokeratin expression such as pancytokeratin, AE1/AE3, or Cam5.2) according to the assessment documented in the “Disease History” eCRF page.
- No active central nervous system (CNS) metastases; subjects with a history of treated CNS metastases (by surgery or radiation therapy) must have fully recovered from treatment, demonstrated no progression for at least 2 months, and not require continued steroid therapy.

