 - = Last day of the month, if both Year and Month are available and Year = Year of min (EOT date, death date) and Month < the month of min (EOT date, death date)
 - = min (EOT date, death date), for all other cases

Date of last contact

The last contact date will be the latest complete date among the following, up to the cut-off date for the analysis:

- All subject assessment dates (blood draws (laboratory, PK), vital signs, performance status, ECG, tumor assessments)
- Start and end dates of anti-cancer therapies administered after study treatment discontinuation
- AE start and end dates
- Date last known to be alive collected on the eCRF form “Subject Status / Survival Follow-up” (only used if status is ‘alive’)
- Study drug start and end dates
- Date of discontinuation from the “Study Termination” eCRF page (do not use if reason for discontinuation is lost to follow-up)

Death date

Missing or partial death dates will be imputed based on the last contact date.

- If the date is completely missing it will be imputed as the day after the date of last contact.
- If the day or month is missing, death will be imputed to the maximum of the full (non-imputed) date of last contact (excluding the date of death) and the following:
 - Missing day: 1st day of the month and year of death
 - Missing day and month: January 1st of the year of death

If the day is missing from the date of last contact it will be imputed to 1st day of the month and year of last contact only if derived from the survival page.

Tumor assessments

The following specifications apply to the determination of tumor assessment date for investigator assessment. For tumor assessments by the IERC, the date of assessment is determined by the IERC as specified in the Charter.

All investigation dates (e.g., X-ray, CT scan, photography) must be completed with day, month, and year.

If there are multiple scan dates associated with an evaluation, i.e., radiological assessments occur over a series of days rather than the same day, the choice of date of assessment could impact the date of progression and/or date of response. If there are multiple scan dates associated with an evaluation, the earliest of the scan dates associated with the evaluation will be used as the date of assessment.

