If one or more investigation dates for an evaluation are incomplete but other investigation dates are available, the incomplete date(s) are not considered for calculation of the assessment date, and assessment date is selected as the earliest of all investigation dates (e.g., X-ray, CT-scan, photography).

If all measurement dates for an evaluation have no day recorded, the 1st of the month is used.

If the month is not completed, for any of the investigations for an evaluation, the respective assessment will be considered to be at the date which is exactly between the previous and the following assessment. If both a previous and following assessment are not available, this assessment will not be used for any calculations.

For IERC-based tumor assessments, the process is a double radiology review with adjudication if needed, and a single oncologist review. The records containing the adjudicated data from the radiologists are used for analysis. In cases where adjudication was not performed (i.e., the two radiologists were in agreement on the timepoint overall response), the record from the radiologist designated as ‘Reader 1’ was used for analysis. This decision applies to the algorithms used to identify subjects with visceral metastases at baseline and lymph node disease at baseline, in addition to all efficacy analyses.

All statistical analyses will be performed using SAS® Version 9.2 or higher.

12 Trial Subjects

The subsections in this section include specifications for reporting subject disposition and treatment/study discontinuations. Procedures for reporting protocol deviations are also provided.

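### Does the Part B SAP drop the oncologist review from the IERC-determined endpoints by analysing only radiologist records?

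*SAP*

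**What the plan says.** Protocol Section 2.3.2 sets up the Part B committee as "a double radiology review with adjudication and single oncologist review". Its task is to review imaging and physical findings, including skin lesion mapping, "for the determination of the BOR and date of disease progression for each subject". The same section leaves the committee's membership, mandate and processes to the IERC charter. Protocol Section 7.3 adds: "The IERC will make the determination as to whether the criteria for tumor response or progression according to RECIST 1.1 have been met".

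The primary endpoint for Part B, in protocol Section 8.3.1, is an objective response "determined by an IERC, with a duration of at least 6 months". Part B SAP Section 16.1 uses the same definition, and SAP Section 16.2.2 takes the response at each visit as the one adjudicated by the IERC.

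Part B SAP Section 11, under tumor assessments, repeats the three-step process and then fixes the data source: "The records containing the adjudicated data from the radiologists are used for analysis". Where there was no adjudication because the two radiologists agreed on the timepoint response, the Reader 1 record is taken. The rule covers the algorithms for visceral metastases and "lymph node disease at baseline, in addition to all efficacy analyses". On dates, the same section states: "For tumor assessments by the IERC, the date of assessment is determined by the IERC as specified in the Charter". SAP Section 9 declares no departure from the protocol: "The statistical methods as described in the protocol for Part B of this study were adopted".

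**The concern.** Every record that Section 11 selects belongs to a radiologist. The oncologist review is named in one sentence and then tied to no analysed record. A programmer who followed the paragraph literally, with nothing else to hand, would build DRR, best overall response, duration of response, PFS, response status and time to response from radiology data alone. If the oncologist's decision were stored separately and could change the radiology result, the report would carry a radiology-only DRR labelled as an IERC result, and Section 9 would not mention it.

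The stakes would be real. Protocol Section 5.1 says Part B is the confirmatory study for some approvals. Skin findings also matter in this disease: protocol Section 7.3 allows skin lesions as target lesions and counts new cutaneous lesions as progression. Overall survival is not determined by the committee and is unaffected.

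**Working it through.** **Step 1. What the Section 11 rule has to solve.** A double read gives two radiology records per timepoint, and three when a disagreement is adjudicated. The analysis needs one. Agreement is defined on the timepoint overall response, so two agreeing readers may still have chosen or measured different lesions, and a tie-break is needed even then. The rule supplies it: 1 of 3 (the adjudicated record) or 1 of 2 (Reader 1). A single oncologist review creates no duplicates and needs no tie-break. The inclusion of visceral and lymph-node status at baseline fits this reading, because those are lesion-location data that come from the radiology reads.

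**Step 2. Which text defines the outcome.**

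| Place | Source of the outcome |
|---|---|
| Protocol 7.3 | the committee |
| Protocol 8.3.1 and 8.5.2 (DRR) | the IERC |
| Part B SAP 16.1 (DRR) | the IERC |
| Part B SAP 16.2.2 (visit response, BOR) | adjudicated by the IERC |
| Part B SAP 16.2.5 and 16.4.1 (response status, time to response) | the IERC |
| Part B SAP 11 | which radiology record is used |

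The endpoint sections name the committee. Section 11 can be read as saying where its data are found, without redefining the endpoint.

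**Step 3. Where the oncologist's role belongs.** Protocol 2.3.2 sends committee processes to the charter. Protocol 8.3.1 sends the response date there. Protocol 8.3.2 and SAP 16.2.4 do the same for the first progression date, as SAP 11 and 16.2.2 do for assessment dates. How an oncologist review combines with radiology reads is a committee process. The protocol lists the review as a step and does not say that it overrides or finalises the radiology result. Protocol Section 8 contains no reader-record rule that SAP Section 9 would have to list as changed.

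**Step 4. Scale.** Inputs: n = 112 and an assumed DRR of 45% (SAP Section 7), with two-sided 95% Clopper-Pearson limits (SAP 16.1). For x responders,

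- lower limit = Beta quantile (0.025; x, n − x + 1)
- upper limit = Beta quantile (0.975; x + 1, n − x)

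The plan's own figures reproduce: 32/112 gives (20.4; 37.9), 45/112 gives (31.0; 49.9) and 50/112 gives (35.2; 54.3). The lower limit exceeds 20% from 32 responders, with probability 99.99% at a true DRR of 45% (plan: above 99%). It exceeds 30% from 44 responders, with probability 90.6% (plan: 90%).

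One net reclassified subject moves DRR by 1/112 = 0.89 points:

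| Durable responders | DRR | 95% CI |
|---|---|---|
| 49 | 43.8% | 34.4 to 53.4 |
| 50 | 44.6% | 35.2 to 54.3 |
| 51 | 45.5% | 36.1 to 55.2 |

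The plan also compares 45/112 with the upper limit of the historical series, 29.5%. One net loss gives 44/112, with a lower limit of 30.2%. Two give 43/112, with 29.4%, just under that reference. These counts are assumed. They would apply to any reclassification from any cause and say nothing about whether this rule produces one.

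**The case for a change.** The best argument for acting is that the SAP should stand on its own for the source of a confirmatory primary endpoint. Section 11 defers assessment dates to the charter but states the response record itself, so a literal reader has no prompt to look further. The reader who brings skin photographs and physical findings together with the scans may well be the oncologist. A reader of the SAP cannot tell from it whether the selected record is the committee's final determination, and one sentence would settle the matter.

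What stands is that the role of the oncologist review is not written down in the SAP. The rest does not follow from the documents. That the oncologist integrates the skin findings is an inference. That the oncologist's result is a separate record, and one that can overturn the radiology read, is not stated anywhere. Reporting radiology-only results as a sensitivity analysis, or declaring a departure in Section 9, would make sense only if both were true. If the oncologist's review already feeds the record that the vendor delivers, following Section 11 gives the IERC result exactly.

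**Conclusion.** No change is called for. This is a gap in description that the trial's analysts, working with the charter and the vendor's data specification, would fill in the ordinary course. The endpoint definitions tell them that the outcome is the committee's determination, and Section 11 tells them which of several radiology reads to take. Following the plan is not shown to give a wrong DRR, best overall response or progression date.

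The size of any effect is unknown, because no disagreement rate is given. One net subject would shift DRR by 0.9 points in either direction, and Part B is an estimation study without a success rule.

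The conclusion assumes that the charter does not make the oncologist's result a separate, final record that differs from the radiology record. If it does, the endpoint definitions in Sections 16.1 and 16.2.2 already make the committee's determination the analysed outcome, so that record would be the source.
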